6.2.3 Recommended treatment for MS relapses

The decision to treat MS relapses should be based on the Investigator's judgement and/or local clinical practices. If MS relapses require treatment, the standard treatment should consist of a short course of corticosteroids (methylprednisolone). Standard of care will be followed during treatment.

Taper with oral steroids is not permitted. Plasmapheresis may be used only if subject does not respond to standard treatment with corticosteroids.

Investigators should consider the added immunosuppressive effects of corticosteroid therapy and increase vigilance regarding infections during such treatment and in the weeks following administration.

Use of steroids for treatment of relapses must be recorded on the Concomitant medications eCRF.

Please refer to restrictions for MRI in [Section 8.3.2](#) concerning the use of steroids and performing the MRI.

6.3 Preparation and dispensation

Each study site will be supplied with study drug in packaging as described in [Section 6.1.1](#).

Ofatumumab is commercially available and will be supplied locally by the Novartis Country Organization (CO). Preparation and dispensation should follow the locally approved package insert and local practice.

As per [Section 4.6](#), during a Public Health Emergency as declared by local or regional authorities, i.e. pandemic, epidemic or natural disaster, that limits or prevents on-site study visits, delivery of IMP directly to a participant's home may be permitted (if allowed by local or regional health authorities and ethics committees as appropriate) in the event the Investigator has decided that an on-site visit by the participant is no longer appropriate or possible, and that it is in the interest of the participant's health to administer the study treatment even without performing an on-site visit. The dispatch of IMP from the site to the participant's home remains under the accountability of the Investigator. Each shipment/provisioning will be for a maximum of 4 months' supply. In this case, additional phone calls or virtual contacts to replace scheduled on-site visits will occur between the site and their participants for instructional purposes, safety monitoring, drug accountability, investigation of any adverse events, ensuring participants

continue to benefit from treatment and discussion of the participants' health status until the participants can resume visits at the study site.

6.3.1 Handling of study treatment and other treatment

6.3.1.1 Handling of study treatment

Study treatment must be received [REDACTED], handled and stored safely and properly and kept in a secured location to which only the investigator and designated site personnel have access. Upon receipt, all study treatment must be stored according to the instructions specified on the approved label.

Clinical supplies are to be dispensed only in accordance with the protocol. Technical complaints are to be reported to the respective Novartis CO Quality Assurance.

Medication labels will be in the local language and comply with the legal requirements of each country. They will include storage conditions for the study treatment but no information about the participant except for the medication number.

The Investigator must maintain an accurate record of the shipment and dispensing of study treatment in a drug accountability log. Monitoring of drug accountability will be performed by field monitors during site or remote monitoring visits, and at the completion of the trial.

If study treatment is administered at home, participants will be asked to return all unused study treatment and packaging at the end of the study or at the time of discontinuation of study treatment.

The site may destroy and document destruction of unused study treatment, drug labels and packaging as appropriate in compliance with site processes, monitoring processes, and per local regulation/guidelines. Otherwise, the investigator will return all unused study treatment, packaging, drug labels, and a copy of the completed drug accountability log to the Novartis monitor or to the Novartis address provided in the investigator folder at each site.

6.3.2 Instruction for prescribing and taking study treatment

Ofatumumab will be dispensed starting at W0, and then at scheduled visits throughout the Treatment period according to [Table 8-1](#).

Participants will receive 3 initial s.c. injections of ofatumumab at W0, W1 and W2, followed by subsequent regular monthly dosing starting at W4 (a month is defined as 28 days).

The first s.c. injection at W0 will be administered [REDACTED]

[REDACTED]

[REDACTED]

Participants, who miss s.c. injections or temporarily interrupt study drug without discontinuing from the study or withdrawing consent, will be permitted to resume study drug if determined to be safe and appropriate in the opinion of the Investigator. When resuming study drug, the timing of the next s.c. injection will be determined based on the original study schedule as follows:

- If one monthly injection is missed by more than 1 week, the participant should skip the dose and take the next dose at the time when the next injection would be due according to the original schedule.
- If two or more consecutive monthly injections are missed, the Investigator should inform the local Sponsor Medical Advisor before re-starting dosing.
- If any initial dose (at W0, W1 or W2), or the W4 dose is missed, then the injection should be administered as soon as possible. The next injection should then be administered according to the original schedule.

All dosages prescribed to the participant and all dose administrations and interruptions during the study must be recorded on the eCRF.

6.4 Participant numbering, treatment assignment, randomization

6.4.1 Participant numbering

Each participant is identified in the study by a Participant Number (Participant No.), that is assigned when the participant is enrolled for screening and is retained for the participant throughout his/her participation in the trial. A new Participant No. will be assigned at every subsequent enrollment if the participant is re-screened. The Participant No. consists of the Center Number (Center No.) (as assigned by Novartis to the investigative site) with a sequential Participant No. suffixed to it, so that each participant's participation is numbered uniquely across the entire database. Upon signing the informed consent form (ICF), the participant is assigned to the next sequential Participant No. available.

6.4.2 Treatment assignment, randomization

This is a single-arm study and all participants will receive the same treatment (ofatumumab 20 mg s.c.).

6.5 Treatment blinding

Not applicable.

6.6 Dose escalation and dose modification

Study treatment dose adjustments are not permitted during the study. Interruptions are permitted if clinically indicated.

Conditions/events that may lead to the study drug interruptions based on Investigator judgment and overall clinical assessment include:

- reported serious adverse event;
- emergency medical condition, unplanned hospitalization, involving use of excluded concomitant medications;
- abnormal laboratory value(s) or abnormal test or examination result(s).

Should the participant interrupt the study drug for whatever reason, re-start decision should be made on a case-by-case basis. Should the Investigator decide, after informing the Sponsor, to re-initiate treatment with study drug, depending on the duration of the interruption, the first s.c. dose at re-start may need to take place [REDACTED] to ensure observation in a similar manner as W0.

The reason for the interruption of treatment and date of interruption should be appropriately documented in the source documents as well as in the eCRF.

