6.2.2 Prohibited medication

Use of the treatments displayed in the below table is not allowed concomitantly with study treatment.

Exclusionary medications for study eligibility are listed in the exclusion criteria ([Section 5.2](#)).

Use of excluded medications is not allowed while the participant is on study treatment.

Table 6-2 Prohibited medication

Medication	Action taken
Any immunosuppressive/ chemotherapeutic medications or procedures including but not limited to cyclosporine, azathioprine, methotrexate, cyclophosphamide, mitoxantrone, lymphoid irradiation and hematopoietic stem cell transplantation; monoclonal antibodies targeting the immune system including but not limited to natalizumab, alemtuzumab, daclizumab and B-cell depleting agents such as but not limited to rituximab, ocrelizumab, obinutuzumab and BTK inhibitors.	Discontinue study treatment; increase vigilance regarding infections. NOTE: Restarting study treatment is not permitted.
Systemic corticosteroids except when given for symptomatic treatment of MS relapses or as pre-medication Immunoglobulins	Interrupt study treatment; increase vigilance regarding infections.
Any other immunomodulatory or disease-modifying MS treatment, including but not limited to fingolimod, siponimod, interferon beta, glatiramer acetate, dimethyl fumarate	Discontinue study treatment; increase vigilance regarding infections. NOTE: Restarting study treatment is not permitted.

Medication	Action taken
Any other investigational drugs	Discontinue study treatment; increase vigilance regarding infections. NOTE: Restarting study treatment is not permitted.
Administration of any live or live-attenuated vaccine on study drug (long-lasting effects of ofatumumab should be taken into consideration; refer to Investigator's Brochure).	They may be administered when participants are no longer exposed to study drug (Section 16.4.4). Consider risk/benefit and follow local labels. Note: Restarting study treatment is not permitted.

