9.1 Discontinuation from study treatment and from study

9.1.1 Discontinuation from study treatment

Discontinuation of study treatment for a participant occurs when study treatment is permanently stopped for any reason (prior to the planned completion of study drug administration, if any) and can be initiated by either the participant or the Investigator.

The Investigator must discontinue study treatment for a given participant if he/she believes that continuation would negatively impact the participant's well-being.

Discontinuation from study treatment is required under the following circumstances:

- Participant/guardian decision ([Section 9.1.2](#))
- Pregnancy ([Section 8.4.3](#) and [Section 10.1.4](#))
- Use of prohibited treatment as per recommendations in the prohibited treatment section ([Section 6.2.2](#))
- Diagnosis of PML ([Section 16.4.1](#))
- Hypersensitivity to the study drug

- Protocol violation that results in a significant risk to the participant's safety
- Emergence of certain adverse events, such as malignancy (except successfully treated basal cell carcinoma, in situ squamous cell carcinoma and in situ carcinoma of cervix of uterus), liver failure, or serious chronic infection (such as active hepatitis B, HIV)
- Laboratory abnormalities requiring the action of study drug discontinuation as defined in [Section 16.1](#)
- Any laboratory abnormalities that in the judgment of the Investigator, taking into consideration the participant's overall status, prevents the participant from continuing participation in the study
- Any situation in which study participation might result in a safety risk to the participant
- Non-compliance with study drug or study procedures

If discontinuation of study treatment occurs, the Investigator should make a reasonable effort to understand the primary reason for the participant's premature discontinuation of study treatment and record this information.

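### Protocol Section 6.6 allows interruption and case-by-case restart after emergency use of any excluded medication, while Table 6-2 and Section 9.1.1 bar restart for most medication classes

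*Protocol*

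**What the plan says.** Three parts of the protocol govern this situation.

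- **Section 6.6** permits interruptions. It opens its list with "Conditions/events that may lead to the study drug interruptions based on Investigator judgment and overall clinical assessment include" and includes "emergency medical condition, unplanned hospitalization, involving use of excluded concomitant medications". It continues: "Should the participant interrupt the study drug for whatever reason, re-start decision should be made on a case-by-case basis". Re-initiation is the Investigator's decision after informing the sponsor.
- **Section 6.2.2** states the general rule: "Use of excluded medications is not allowed while the participant is on study treatment". Table 6-2 then gives an action for each class. For three rows the action is to discontinue, with the remark "NOTE: Restarting study treatment is not permitted". The live-vaccine row carries the same bar on restart but does not use the word discontinue. The entry for systemic corticosteroids (outside relapse treatment and premedication) and immunoglobulins reads "Interrupt study treatment; increase vigilance regarding infections".
- **Section 9.1.1** defines discontinuation as a permanent stop. Under the lead-in "Discontinuation from study treatment is required under the following circumstances" it lists "Use of prohibited treatment as per recommendations in the prohibited treatment section", so what is mandatory follows the actions in Table 6-2.

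None of the three sections states an exception for emergencies or says which text prevails.

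**The concern.** The event in Section 6.6 is a likely setting for an excluded drug to be given outside the site's control: an acute admission, possibly under another clinical team. A site that consults Section 6.6 at that point finds a discretionary interruption and an open restart decision. A site that consults Table 6-2 finds, for most classes, that restart is barred.

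Two things are at stake.

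- **Safety.** The protocol itself warns about added immunosuppression (Sections 6.2.3 and 9.3). The two texts diverge for the drugs to which that warning is most relevant.
- **Classification.** Premature discontinuation triggers an End of Study visit as soon as possible (Protocol Sections 3 and 8). SAP Section 2.5.1 ends both relapse counting and time in study at the end of the treatment period. SAP Section 2.4.1 subtracts interruptions from exposure, which lowers compliance, but does not treat premature discontinuation as non-compliance. The last dose date moves the 100-day safety cut-off (SAP Section 2.1.1). The analyses in SAP Section 2.7.5 include only participants who discontinued prematurely. Two participants with the same event could therefore be handled differently in several outputs.

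**Working it through.** The plan gives no figure to reproduce on this point. The check compares the texts, followed by a bound on the effect on the primary endpoint.

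**Step 1. Section 6.6 against each entry of Table 6-2**

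| Table 6-2 entry | Action in Table 6-2 | Restart in Table 6-2 | Section 6.6 |
|---|---|---|---|
| Immunosuppressive/chemotherapeutic agents or procedures; immune-targeting antibodies | Discontinue | Not permitted | May interrupt; restart case by case |
| Systemic corticosteroids (with exceptions); immunoglobulins | Interrupt | No bar | May interrupt; restart case by case |
| Other immunomodulatory or MS disease-modifying treatment | Discontinue | Not permitted | May interrupt; restart case by case |
| Other investigational drugs | Discontinue | Not permitted | May interrupt; restart case by case |
| Live or live-attenuated vaccine | Give only when no longer exposed to study drug | Not permitted | May interrupt; restart case by case |

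The explicit instruction to discontinue appears in three of five rows, and the bar on restart in four of five. If corticosteroids and immunoglobulins are two separate rows, the counts are three of six and four of six. In the corticosteroid and immunoglobulin entry the two texts agree, apart from Section 6.6 saying may where the table states an action.

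**Step 2. Does the word excluded narrow Section 6.6?** Section 6.2.2 points to Section 5.2 for exclusionary medications. Criterion 13 there covers other investigational drugs and criterion 14 covers live vaccines. Criterion 15 covers MS disease-modifying therapies, corticosteroids, intravenous immunoglobulin, immunosuppressants and antibodies such as natalizumab and ocrelizumab. So even if excluded means the Section 5.2 list, it reaches every entry of Table 6-2.

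**Step 3. Upper bound on the effect on ARR person-time**

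Inputs: Month 12 at Day 336 (Protocol Table 8-1); time in study = (end of treatment period date − first dose date + 1)/365.25 (SAP Section 2.5.1); 85 completers among about 100 participants and ARR 0.15 (Protocol Section 12.8.1). Assumption not in the documents: the 15 dropouts leave halfway on average.

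- Time in study of a completer: (336 + 1)/365.25 = 0.92 years.
- Total person-time: 85 × 0.92 + 15 × 0.46 = 78.2 + 6.9 = 85.1, about 85 person-years.
- Most that one participant can lose, if discontinued at about Day 1: 0.92/85 = 1.1% of person-time.
- Expected relapses in that time: 0.15 × 0.92 = 0.14.
- Discontinuation at mid-study halves both: about 0.5% and 0.07 relapses.

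The documents do not say how often an excluded medication would be given in an emergency, so these per-participant figures cannot be turned into a total.

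**The case against.** The strongest reply is that the protocol keeps interruption and discontinuation apart. The restart sentence in Section 6.6 applies to a participant who has interrupted. Someone discontinued under Table 6-2 has not interrupted, so the sentence need not reach that person. On this reading Section 6.6 serves the corticosteroid and immunoglobulin classes, where the table itself says interrupt and Section 16.4.3 leaves re-initiation after interruption to the Investigator. There are safeguards too. Section 6.2.1 requires each concomitant drug to be assessed against the exclusion criteria and prohibited medication, with sponsor contact if in doubt. Section 6.6 requires the sponsor to be informed before re-initiation.

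Part of this stands. The harmonised reading is possible, and the sponsor contacts make an unnoticed restart less likely. But Section 6.6 states no such limit: it places use of excluded medication under interruption without naming a class. Section 6.3.2 is also permissive, letting participants resume after an interruption if the Investigator finds it safe and appropriate, and it does not mention Table 6-2 either. Sponsor contact lowers the risk but does not settle which rule applies.

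A reader might infer that Section 6.6 directs restart. It does not: it permits restart, and a case-by-case decision can apply the bar in Table 6-2. Nor do four rows call for discontinuation in words: three do, and the live-vaccine row only bars restart. The number of rows also says nothing about how often sites would meet the conflict, since the Section 6.6 trigger is tied to emergencies and unplanned hospitalization.

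**Conclusion.** The inconsistency is real. For the three discontinue rows and the live-vaccine row, Section 6.6 leaves open a restart that Table 6-2 forbids; for the three discontinue rows it also makes discretionary a stop that Section 9.1.1 makes mandatory. Corticosteroids and immunoglobulins are not in conflict on the action.

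The weight of the point is participant safety and uniform classification of discontinuation and the End of Study date. A reader might go further and infer a biased primary result. The documents do not support that. The ceiling is about 1% of person-time per affected participant, time and relapses before discontinuation are kept, and the log-time offset accounts for unequal follow-up under the plan's stated assumption of non-informative drop-out. The ceiling rests on the planned 85 completers and the assumed mid-study dropout time. No material effect on ARR is claimed, and no view is taken on which clinical rule is right.

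**What to change.** Reconcile Section 6.6 with Table 6-2 and Section 9.1.1. State in Section 6.6 which medication classes its interruption and restart text covers, and refer to Table 6-2 for all others. The same pointer in Section 6.3.2 would close the second permissive text. The sponsor's clinical team decides the action for each class.

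The cost is a sentence or two of protocol wording or a clarification to investigators, with no change to data collection or analysis. If treatment has already ended, the sponsor can identify from the concomitant medication and dosing records the participants who received an excluded medication, and report whether each was interrupted, restarted or discontinued.

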6.7 Additional treatment guidance

6.7.1 Treatment compliance

The Investigator must promote compliance by instructing the participant to take the study treatment exactly as prescribed and by stating that compliance is necessary for the participant's safety and the validity of the study. The participant must also be instructed to contact the Investigator if he/she is unable for any reason to take the study treatment as prescribed. A monitor will perform and document drug accountability during site visits and at the end of the study. All study treatment dispensed and returned must be recorded in the drug accountability log.

7 Informed consent procedures

Eligible participants may only be included in the study after providing (witnessed, where required by law or regulation) IRB/IEC-approved informed consent.

If applicable, in cases where the participant's representative(s) gives consent (if allowed according to local requirements), the participant must be informed about the study to the extent possible given his/her level of understanding. If the participant is capable of doing so, he/she

must indicate agreement by personally signing and dating the written informed consent document.

Informed consent must be obtained before conducting any study-specific procedures (e.g. all of the procedures described in the protocol). The process of obtaining informed consent must be documented in the participant source documents.

Novartis will provide to investigators in a separate document a proposed informed consent form (ICF) that complies with the ICH E6 GCP guidelines and regulatory requirements and is considered appropriate for this study. Any changes to the proposed consent form suggested by the investigator must be agreed by Novartis before submission to the IRB/IEC.

Information about common side effects already known about the investigational treatment can be found in the Investigator's Brochure (IB) and the approved label. This information will be included in the participant informed consent and should be discussed with the participant during the study as needed. Any new information regarding the safety profile of the investigational drug that is identified between IB updates will be communicated as appropriate, for example, via an investigator notification or an aggregate safety finding. New information might require an update to the informed consent and then must be discussed with the participant.

The following informed consents are included in this study:

- Main study consent, which also includes:
 - A subsection that requires a separate signature for the 'Optional Consent for Additional Research' to allow future research on data/samples collected during this study
 - As applicable, Pregnancy Outcomes Reporting Consent for female participants who took study treatment

Women of child bearing potential must be informed that taking the study treatment may involve unknown risks to the fetus if pregnancy were to occur during the study and agree that in order to participate in the study they must adhere to the contraception requirements.

A copy of the approved version of all consent forms must be provided to Novartis after IRB/IEC approval.

Participants might be asked to complete an optional questionnaire to provide feedback on their clinical trial experience.

As per [Section 4.6](#), during a Public Health Emergency as declared by local or regional authorities i.e. pandemic, epidemic or natural disaster, that may challenge the ability to obtain a standard written informed consent due to limits that prevent an on-site visit, Investigator may conduct the informed consent discussion remotely (e.g. telephone, videoconference) if allowable by a local health authority.

Guidance issued by local regulatory bodies on this aspect prevail and must be implemented and appropriately documented (e.g. the presence of an impartial witness, sign/dating separate ICFs by trial participant and person obtaining informed consent etc.).

8 Visit schedule and assessments

The Assessment Schedule ([Table 8-1](#) and [Table 8-2](#)) lists all of the assessments and indicates with "X" or "S" when they are performed. The "X" in the table denotes the assessments to be recorded in the clinical database or received electronically from a vendor. The "S" in the table denotes the assessments that are only in the participant's source documentation and do not need to be recorded in the clinical database. All data obtained from these assessments must be supported in the participant's source documentation.

Participants should be seen for all visits/assessments as outlined in the assessment schedule ([Table 8-1](#) and [Table 8-2](#)) or as close to the designated day/time as possible, with an allowed "injection window" as described in [Section 6.3.2](#). Missed or rescheduled visits should not lead to automatic discontinuation. In the study, one month is defined as 28 calendar days.

For all scheduled visits, any AE or SAE reported by the participant will be recorded according to [Section 10.1.1](#) and [Section 10.1.2](#). For women of childbearing potential, urine or serum pregnancy test is required prior to each administration of study drug, and drug administration can only be conducted with negative pregnancy test result (refer to [Section 8.4.3](#)).

EOS visit is mandatory for all participants. The EOS visit is conducted at the end of the Treatment period (i.e. M12), or when participants prematurely discontinue study treatment before M12, whether they plan to enter Post-treatment Follow-up period or withdraw from the study. Participants who prematurely discontinue study treatment will have their EOS visit as soon as possible. At the EOS visit, AEs and concomitant medications not previously reported must be recorded on the eCRFs.

Participant diaries

During the study, participants will be asked to complete a diary from BL/W0 onwards till EOS to record information pertinent to study treatment administration (including date and time of s.c. injections), home pregnancy testing (date and results) for women of childbearing potential and other information (e.g. AEs). The participant is requested to bring the completed diaries with them to each visit and the Investigator/Study Coordinator/Nurse must review these for completeness and for potential AEs, injection-related reactions, study treatment interruptions etc. and record information obtained from the diaries into the relevant eCRFs.

Telephone or virtual interviews

Site personnel will conduct a structured telephone interview (script provided) for W1 and W2 initial doses, and then every month in between the scheduled site visits following the W4 site visit ([Table 8-1](#) and [Table 8-2](#)). During the Treatment period, the interview should take place around time of the monthly s.c. self/home-injections to query about any new or worsening symptoms warranting an unscheduled visit, compliance with study treatment, changes in concomitant medication, injection reactions, results of home pregnancy testing and compliance with contraception requirements when applicable. During the Post-treatment Follow-up period, the interview should take place regularly every month between scheduled visits to query about any new or worsening symptoms warranting an unscheduled visit, changes in MS treatment and concomitant medication, compliance with contraception requirements and potential AEs etc.

Participants, except for those who will continue with commercially available ofatumumab treatment, will enter the 6-month Post-treatment Follow-up period after EOS as described in [Table 8-2](#).

As per [Section 4.6](#), during a Public Health Emergency as declared by local or regional authorities i.e. pandemic, epidemic or natural disaster that limits or prevents on-site study visits, alternative methods of providing continuing care may be implemented by the investigator as the situation dictates. If allowable by a local health authority and depending on operational capabilities, phone calls, virtual contacts (e.g. tele consult) or visits by site staff/home nursing staff to the participant's home, can replace on-site study visits, for the duration of the disruption until it is safe for the participant to visit the site again.

Table 8-1 Assessment Schedule, Screening and treatment

Period	Screening	Treatment							Treatment	
Visit Name	Screening	BL/W0	W1 (Phone Interview)	W2 (Phone Interview)	W4	M3	M6	M9	M12/EOS	Unscheduled Visit ¹
Days	-30 to -1	-	7	14	28	84	168	252	336	-
Informed consent	X									
Demography, Height	X									
Inclusion / Exclusion criteria	X	X ²								
Medical history/current medical conditions	X									
MS History/Treatments	X									
COVID-19 vaccination status	X	X ³	X	X	X	X	X	X		
Physical Examination	S	S ³			S		S		S	S
Weight, Vital Signs	X	X ⁴			X	X	X	X	X	X
Electrocardiogram (ECG)	X									
Hematology	X ⁵				X	X	X	X	X	
Clinical Chemistry	X ⁵				X	X	X	X	X	
Urinalysis	X ⁵				X		X		X	
Serological markers for hepatitis B ⁶	X ⁵									
HIV antibody screen ⁷	X ⁵									
Syphilis screen ⁷	X ⁵									
Tuberculosis screen ⁷	X ⁵									
Pregnancy and assessments of fertility ⁸	X ⁵	X ³			X	X	X	X	X	
Contraception Status ⁹	X	X ³	X	X	X	X	X	X	X	
MS relapse	X	X ³	X	X	X	X	X	X	X	X
MRI	X					X			X ¹⁰	

Period	Treatment										Treatment
	Screening	BL/W0	W1 (Phone Interview)	W2 (Phone Interview)	W4	M3	M6	M9	M12/EOS	Unscheduled Visit ¹	
Visit Name	Screening										
Days	-30 to -1	-	7	14	28	84	168	252	336	-	
Adverse Events	X	X ³	X	X	X	X	X	X	X	X	
Prior/Concomitant Medications ¹¹	X	X ³	X	X	X	X	X	X	X	X	
Surgical/medical procedures	X	X ³	X	X	X	X	X	X	X	X	
Sample for B-cells ¹²	X	X ³			X	X	X		X		
Sample for IgG and IgM ¹²	X						X		X		
Drug dispensation		S			S	S	S	S			
Drug administration ¹³		X	X	X	Monthly, except for M12/EOS						
Participant diaries ¹⁴					X						
Participant Diary Review					X	X	X	X	X		
Phone interview/virtual visit ^{15,16}			X	X	Monthly between scheduled visits						
Treatment Phase Completion									X		

¹ Assessment to be recorded in the clinical database or received electronically from a vendor

² Assessment to be recorded in the source documentation only

³ Unscheduled visit: assessments performed as unscheduled visits will depend on the clinical needs of the participant. All participants with neurological symptoms suggestive of an MS relapse should at least have the mentioned assessments in table 8-1 performed. Other assessments may be done as appropriate.

⁴ Inclusion/exclusion criteria need to be checked again before first dose of study drug.

⁵ Assessments to be completed prior to first study drug administration.

⁶ Vital signs should be obtained 30-60 min before sc injection (if premedication is administered, pre-injection vital signs should be obtained before premedication is administered).

⁷ Laboratory results must be available prior to Baseline/Week 0 (BL/W0) to evaluate the Inclusion/Exclusion criteria.

⁸ Hepatitis B screening is required in all study participants, including hepatitis B surface antigen (HBsAg) and hepatitis B core antibody (HBcAb) testing. These can be complemented with other appropriate markers as per local guidelines. For detailed guidance, refer to [Section 16.4.2](#).

⁹ HIV, Syphilis and Tuberculosis testing must be done at central lab as part of eligibility check (Exclusion criterion #6 and #9) for all participants.

¹⁰ Women of childbearing potential only -For Screening and EOS visits, serum pregnancy test will be conducted in central lab. Monthly urine pregnancy tests will be conducted between scheduled visits(starting after W4) at home or at site prior to the administration of study treatment. In case of a positive test result, the participant must contact the investigator immediately and confirmatory testing should be performed at the investigator's discretion.

¹¹ Contraception MUST be used during the study treatment period and for at least 6 months after the last dose of study drug. Participant's contraception status must be reviewed and documented to ensure method of contraception continues to be appropriate per protocol requirement for effective contraception.

Period	Screening	Treatment								Treatment
		BL/W0	W1 (Phone Interview)	W2 (Phone Interview)	W4	M3	M6	M9	M12/EOS	
Visit Name	Screening	-	7	14	28	84	168	252	336	Unscheduled Visit ¹
Days	-30 to -1	-	7	14	28	84	168	252	336	-

¹⁰ MRI scan at the End of Study (EOS) is needed if there was no MRI scan in the last 3 months.

¹¹ Including corticosteroids used to treat MS relapse; any newly started MS treatment as applicable (for participants who have discontinued study medication).

¹² The assessments (samples taken for IgG and IgM, B-cells) should be completed prior to study drug administration.

¹³ The first s.c. injection at W0 will be administered [REDACTED]

¹⁴ Study treatment administration (including date and time of s.c. injections) and home pregnancy testing (date and results) for women of childbearing potential will be recorded for each home injection. Other information (e.g. AEs) will be recorded continuously.

¹⁵ Phone interview will be performed by site staff for W1 and W2, and then every month starting from W4 between scheduled visits. The interview should take place around time of the monthly s.c. self/home injection to query about any new or worsening symptoms warranting an unscheduled visit, injection reactions, results of home pregnancy testing and compliance with contraception requirements.

¹⁶ Phone interview/virtual visits are also applicable to the scheduled visits for participants who exceptionally cannot come to the study site for a face-to-face examination due to a Public Health Emergency (e.g. restricting the subject's general access to sites).

Table 8-2 Assessment Schedule, Post-Treatment Follow-up

Period	Post-Treatment Follow-Up		
Visit Name	V1 ¹	End of FU ^{1,2}	Unscheduled Visit ³
Days	EOS+3 months	EOS+6 months	NA
Weight, Vital Signs	X	X	X
COVID-19 vaccination status	X	X	
Physical Examination	S	S	S
Clinical Chemistry	X	X	
Hematology	X	X	
Urinalysis	X	X	
Pregnancy Test (serum) ⁴	X	X	
Contraception Status ⁵	X	X	
Sample for B-cells	X	X	
Sample for IgG and IgM	X	X	
MS relapse	X	X	X
MRI		X ⁶	
Concomitant medications ⁷	X	X	X
Surgical/medical procedures	X	X	X
Adverse Events	X	X	X
Phone interview/virtual visit ^{8,9}	Monthly between scheduled visits		
Post Treatment Part Completion		X	

^X Assessment to be recorded in the clinical database or received electronically from a vendor

^S Assessment to be recorded in the source documentation only

¹ Visits 1 and end of FU are applicable to all participants, except for completers of the Treatment period who decide to continue with commercially available ofatumumab treatment.

² If a participant prematurely discontinues from the Post-Treatment Follow-up (PT FU), the End of PT FU should be done as soon as possible. If scheduled PT FU1 visit and the end of PT FU visit occur around the same time, only end of PT FU should be done.

³ Unscheduled visit: assessments performed at unscheduled visits depend on the clinical needs of the participant. All participants with neurological symptoms suggestive of an MS relapse should have an EDSS evaluation. Other assessments may be done as appropriate.

⁴ Women of childbearing potential only. Serum pregnancy tests will be conducted on scheduled visits every 3 months by central lab.

Period	Post-Treatment Follow-Up		
	Visit Name	V1 ¹	End of FU ^{1,2}
Days	EOS+3 months	EOS+6 months	NA

⁵ Contraception MUST be used during the study and for at least 6 months after stopping study drug. Participant's contraception status must be reviewed and documented to ensure method of contraception continues to be appropriate per protocol requirement for highly effective contraception.

⁶ For treatment period completers, MRI at the end of PT FU is not needed. For participants that prematurely discontinue from study treatment, MRI scan at the End of FU is needed if there has been no MRI scan in the last 3 months.

⁷ Including corticosteroids used to treat MS relapse; any newly started MS treatment as applicable (for participants who have discontinued study medication).

⁸ Phone interview/virtual visits are also applicable to the scheduled visits for participants who exceptionally cannot come to the study site for a face-to-face examination due to a Public Health Emergency (e.g. restricting the subject's general access to sites).

⁹ Phone interview will be performed by site staff regularly every month between scheduled visits to query about any new or worsening symptoms warranting an unscheduled visit, changes in MS treatment and concomitant medication, compliance with contraception requirements and potential AEs.

